8.3 Imaging Outcomes Analysis

DSA is the reference standard imaging modality for aneurysm assessment after coiling, but MRA imaging is safer for patients and less expensive. Therefore, an imaging outcomes analysis will assess how successfully MRA scans detect residual aneurysm blood flow at final follow-up as compared to DSA scans, based on sensitivity, specificity, and related summary measures.

For each of Raymond-Roy Class II to III (any residual flow), Class II (residual neck), and Class III (residual aneurysm) at the time of final follow-up, the following statistics will be reported using the ITT population and core lab data:

- **Sensitivity:** The proportion of true positives (patients belonging to each of the three Raymond-Roy groups above on DSA) that are correctly identified as such on MRA as well. The percentages of patients assessed as each of Raymond-Roy (1) Class II to III, (2) Class II, and (3) Class III on MRA and DSA out of patients with the same Raymond-Roy group assessed on DSA at the time of final follow-up will be computed.
- **Specificity:** The proportion of true negatives (patients not belonging to each of the three Raymond-Roy groups above on DSA) that are correctly identified as such on MRA as well. The percentages of patients assessed as each of Raymond-Roy (1) Class I, (2) Class I or Class III, and (3) Class I to II on MRA and DSA out of patients with the same Raymond-Roy group assessed on DSA at the time of final follow-up will be computed.
- **Positive likelihood ratio (LR):** Sensitivity divided by (1 - Specificity).
- **Negative likelihood ratio (LR):** (1 - Sensitivity) divided by Specificity.
- **Cohen's κ :** Summary measure of agreement between DSA and MRA in detecting each of Raymond-Roy Class II and III, Class II, and Class III.

As a secondary comparison, this analysis will be repeated using each of Meyers Consensus Grading Scale Grades 1 to 5 (any residual flow), Grade 1 (90% or greater aneurysm occlusion), Grade 2 (70-89% aneurysm occlusion), Grade 3 (50-69% aneurysm occlusion), Grade 4 (25-49% aneurysm occlusion), and Grade 5 (Less than 25% aneurysm occlusion).

8.4 Economic Analysis

Frequency counts and percentages will be reported for the following healthcare utilization data:

- Devices used: Access guide catheters, microcatheters, and Penumbra coils
- Follow-up and additional follow-up clinic and office visits

- Follow-up and additional follow-up DSA, MRA, and CTA scans

The healthcare utilization information will be used to estimate healthcare costs.

8.5 Handling of Multiplicity

There will be no adjustment for multiplicity in SURF study reporting.

9 Subgroup Analysis

The following subgroup analyses will be performed for all primary and secondary effectiveness and safety endpoints using the ITT population:

- **Adjunctive technology used during treatment:** Balloon, Stent, Other, None
- **Age at time of informed consent (years):** < 65, \geq 65
- **Sex:** Female, Male
- **Ethnicity:** Hispanic or Latino, Not Hispanic or Latino
- **Race:** American Indian or Alaska Native, Asian, Black or African American, White, Other
- **Site country:** North America (US/Canada), Europe
- **Target aneurysm location:** Extradural ICA, ICA, ACA, MCA, Posterior Circulation, Other
- **Target aneurysm size:** Small (\leq 5 mm at its largest diameter), Medium (6 to 14 mm at its largest diameter), Large (15 to 24 mm at its largest diameter), Giant (\geq 25 mm at its largest diameter)
- **Target aneurysm status:** Ruptured, Unruptured
- **Target aneurysm anatomical location:** Bifurcation, Sidewall, Other
- **Neck width:** Small-Neck (< 4 mm Neck Width), Wide-Neck (\geq 4 mm Neck Width or Dome-to-Neck Ratio (defined as the maximum of dome width, depth, and height divided by neck width) $<$ 2)
- **Target aneurysm previously treated:** Previous Treatment at Admission, No Previous Treatment at Admission

Descriptive statistics and two-sided 95% Wald confidence intervals will be presented for each subgroup.

10 Safety Analysis

10.1 Primary Safety Analysis

For the primary safety endpoints, frequency counts, percentages, and two-sided 95% Wald confidence intervals will be reported using the ITT population:

- **SAEs up to 24 hours post-procedure:** The percentage of patients who experience serious adverse event(s) with start date on the date of procedure (day 0) or the next calendar day.
- **Device-related SAE up to 7 days or discharge:** The percentage of patients who experience serious adverse event(s) with probable or definite relationship to the SMART Coil System from the date of procedure (day 0) through the date of discharge or seven calendar days from the date of procedure, whichever occurs earlier.

10.2 Secondary Safety Analysis

For the secondary safety endpoints, frequency counts, percentages, and two-sided 95% Wald confidence intervals will be reported using the ITT population:

- **Major ipsilateral stroke:** The percentage of patients who experience major ipsilateral stroke adverse event(s), as defined in the SURF study protocol.
- **Device related SAE at final follow-up:** The percentage of patients who experience serious adverse event(s) with probable or definite relationships to the SMART Coil System from the date of procedure (day 0) through the final follow-up visit at 1 Year \pm 90 Days from the date of procedure.
- **All-cause morbidity and mortality:** The percentage of patients who experience either of the following events:
 - **All-cause morbidity:** mRS 3 to 5 at the final follow-up evaluation or worsening of mRS by 2+ points the date of procedure (day 0) through the final follow-up visit at 1 Year \pm 90 Days from the date of procedure. If the final follow-up mRS is missing, mRS as assessed at the 7-day and/or discharge visit will be substituted.
 - **All-cause mortality:** Death for any reason from the date of procedure (day 0) through calendar day 365

Adverse events occurring after the final follow-up visit at 1 Year \pm 90 Days and deaths occurring after day 365 will be separately tabulated and not included in endpoint and adverse event rates.

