The interim analysis from the first 500 consecutive subjects enrolled included cerebral aneurysms (90.6%, 451/498), of which 31.0% were ruptured; arteriovenous malformations (1.4%); fistulae (4.6%); and other lesions (3.4%)[39]. At admission, 70.8% of subjects were female, and the mean age was 60.0 ± 13.3 years. Aneurysms were small (87.7%), large (12.1%), and giant (0.2%), with 64.2% (265/413) having a wide neck.

The median time of fluoroscopic exposure was 36.5 minutes (IQR 24.0-56.0). Stent-assisted coiling was performed in 29.8% of patients, whereas balloon-assisted coiling was performed in 19.4% of patients. For all aneurysms, the median packing density was 29.5% (IQR 21.4-38.3). For all subjects, adequate occlusion at immediate post-procedure was achieved for 97.6% (483/495). In aneurysm subjects, Raymond I or II was achieved in 79.7% (354/444) of patients at immediate post-procedure, and 88.6% (124/140) at one-year follow-up. The retreatment rate through one-year follow-up was 3.8% (6/157).

Procedural device-related SAEs were observed in 3.2% (16/500) of patients. Mortality rates were 0.4% (2/496) within 24 hours of intervention and 11.4% (21/185) after 24 hours; no deaths were device-related. One-year follow-up data collection is ongoing.

Initial results suggest that the SMART COIL System achieves adequate embolization in a variety of neurovascular lesions. The clinical evidence has shown that coiling is a safe and durable alternative treatment option for suitable subjects. The SURF study will provide additional clinical evidence on the safety and efficacy of the WAVE™ Extra Soft coil (WAVE) for the treatment of cerebral aneurysms.

2. Penumbra SMART COIL System with WAVE Extra Soft Coil

The WAVE Extra Soft Coil is part of the SMART COIL System offered by Penumbra, Inc. and is specifically designed as a filling and finishing coil. WAVE may be used with other SMART Coils that have different sizes and properties: SMART Plus Standard, Standard, Soft, and Extra Soft. The specific coil that is most suitable is determined largely by the morphology of the aneurysm and coil properties needed at various packing stages. The SMART COIL System is designed for endovascular embolization in the neuro and peripheral vasculature. Intended users for this device are physicians who have received appropriate training in interventional radiology.

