16.4.10 Angiographic Outcome

The primary effectiveness endpoint is occlusion of the treated aneurysms. This is defined as the proportion of aneurysms with Class 1 and 2 occlusion as described by Roy et al (*Stroke 2001;32:1998-2004*):

- Class 1 – Complete occlusion
- Class 2 – Residual neck
- Class 3 – Residual aneurysm

Figure 3: Classification of Angiographic Results

Adopted from Roy, Milot and Raymond. Stroke 2001;32:1998-2004

STATISTICAL ANALYSIS PLAN

**SURF: A Prospective, Multicenter Study Assessing the Embolization of
Intracranial Aneurysms using WAVE™ Extra Soft coils, a part of the
Penumbra SMART COIL® System**

Protocol CLP 13669

Version 3.0

Contents

1	Overview	3
2	Sample Size	3
3	Interim Analysis	4
4	Analysis Populations	4
4.1	Definitions	4
5	Statistical Methods	4
6	Baseline Characteristics	5
7	Patient Disposition	5
8	Effectiveness Analysis	5
8.1	Primary Effectiveness Analysis	5
8.2	Secondary Effectiveness Analysis	6
8.3	Imaging Outcomes Analysis	7
8.4	Economic Analysis	7
8.5	Handling of Multiplicity	8
9	Subgroup Analysis	8
10	Safety Analysis	9
10.1	Primary Safety Analysis	9
10.2	Secondary Safety Analysis	9
10.3	Analysis of Adverse Events	10
10.4	Analysis of Deaths	10
11	Pooling Across Centers	10
12	Missing Data and Imputation Methods	11
13	Changes to Planned Analyses	11
14	References	12
15	Revision History	12

1 Overview

SURF is a postmarket, real-world, prospective, multicenter single-arm study. Its objective is to demonstrate the safety and efficacy of the Penumbra SMART COIL® System, including the WAVE™ Extra Soft Coils (WAVE) as a fill and finish coil, in the treatment of intracranial aneurysms. An independent core lab will read images to assess aneurysm occlusion rates, facilitating an analysis on the sensitivity and specificity of MRA imaging to detect residual aneurysm blood flow at final follow-up as compared to DSA (Section 8.3 of this document).

Approximately 800 patients will enroll at up to 60 global sites. Each site will be limited to a maximum enrollment of 120 patients (15% of total enrollment). An estimated 10% of enrolled patients will experience attrition by final follow-up.

This Statistical Analysis Plan (SAP) elaborates on statistical methods outlined in the study protocol and presents analysis conventions. The SAP will be signed off prior to database lock.

2 Sample Size

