Approximately 800 patients will enroll in this post-market study, resulting in 720 patients who achieve final follow-up after 10% anticipated attrition. This sample size provides adequate precision to estimate the primary effectiveness and safety endpoints.

Primary Endpoint	Assumption for Observed Rate ^[1]	95% CI ^[2]	Precision
Adequate occlusion defined as Raymond-Roy Occlusion Class I and II at final follow-up	89% (320/360)	86% to 92%	Greater than $\pm 3.5\%$
	89% (401/450)	86% to 92%	Greater than $\pm 3\%$
	89% (481/540)	86% to 92%	Greater than $\pm 3\%$
	89% (561/630)	87% to 91%	Greater than $\pm 3\%$
	89% (641/720)	87% to 91%	Greater than $\pm 3\%$
Device-related SAE up to 7 days or discharge	2.8% (11/400)	1.1% to 4.4%	Greater than $\pm 2\%$
	2.8% (14/500)	1.4% to 4.2%	Greater than $\pm 1.5\%$
	2.8% (17/600)	1.5% to 4.2%	Greater than $\pm 1.5\%$
	2.9% (20/700)	1.6% to 4.1%	Greater than $\pm 1.5\%$
	2.8% (22/800)	1.6% to 3.9%	Greater than $\pm 1.5\%$
SAEs within 24 hours post-procedure	9.0% (36/400)	6.2% to 11.8%	Greater than $\pm 3\%$
	9.0% (45/500)	6.5% to 11.5%	Greater than $\pm 2.5\%$
	8.8% (53/600)	6.6% to 11.1%	Greater than $\pm 2.5\%$
	8.9% (62/700)	6.8% to 11.0%	Greater than $\pm 2.5\%$
	8.9% (71/800)	6.9% to 10.9%	Greater than $\pm 2.5\%$

^[1] Set at SMART CLP 10023 Registry interim observed results (data on file at sponsor)

^[2] Two-sided 95% Wald normal approximation binomial proportion confidence interval

3 Interim Analysis

As there will be no interim analyses for the purpose of terminating the study early for success or futility, alpha adjustments will not be made to the confidence intervals in the final analysis. However, interim analysis may be performed for the purpose of publication or regulatory submission of SURF results.

4 Analysis Populations

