10.4 Analysis of Deaths

Survival estimates will be used to evaluate the time-to-event using the Kaplan-Meier product-limit method for deaths through 365 days. With the date of procedure set at day 0, any event occurring on or before day 365 will be included. If clinical assessment is missing for a patient who has not died, the patient will be censored at the last follow-up date. Patients who are alive at day 365 will be censored at day 365. The time to death will be plotted with 95% confidence intervals.

Additionally, the frequency and percentage of deaths for any reason (all-cause mortality) will be presented with the two-sided 95% Wald confidence interval.

11 Pooling Across Centers

Analyses will be presented using data pooled across centers. The primary and secondary effectiveness and safety endpoints will be presented by study site to assess any potential site effects.

Pooling analyses will be conducted across study sites on the primary effectiveness and primary safety endpoints. Fisher's exact test (univariate analysis) and stepwise binary logistic regression

on study site, adjusted for key baseline and other appropriate variables (multivariate analysis), will be used. The multivariate results will take precedence in testing for site heterogeneity.

To assess the validity of pooling North America (US/Canada) and Europe sites, logistic regression models will be used for the primary effectiveness and primary safety endpoints. Stepwise multivariate binary logistic regression models with geographic location (North America (US/Canada versus Europe), study site, and a subset of key baseline and procedural predictors will be used for each primary endpoint to test for heterogeneity across geographic locations.

Wald odds ratios of the treatment effects for geographic location and study site will be presented with two-sided p-values to test whether the odds ratios equal 1. Centers enrolling three or fewer patients will be eliminated from all pooling analyses.

12 Missing Data and Imputation Methods

The primary analysis will be data as observed, in which results are reported using the data that are available without imputing missing values.

As sensitivity analyses, the primary effectiveness and primary safety endpoints will be recomputed using the ITT population after imputing missing data:

- Imputation using baseline scores (run for primary effectiveness only)

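### SAP 10.2 reports stroke and later device-related SAEs as crude ITT percentages with no followed-patient denominator or censoring, and no missing-data analysis covers them

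*Combined protocol and SAP*

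**What the plan says.** SAP 10.2 sets the method for all secondary safety endpoints: "For the secondary safety endpoints, frequency counts, percentages, and two-sided 95% Wald confidence intervals will be reported using the ITT population". SAP 4.1 defines ITT as everyone enrolled. The stroke bullet reads "The percentage of patients who experience major ipsilateral stroke adverse event(s), as defined in the SURF study protocol". Neither that bullet nor the definition in protocol 16.4.2 gives a time window. The device-related SAE bullet runs from day 0 to the final visit at 1 year ± 90 days. Neither bullet limits the denominator to patients who were followed.

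The effectiveness sections are written differently. SAP 8.1 and 8.2 also use the ITT population, but they limit the occlusion and retreatment denominators to patients with an evaluation or answer at the time point.

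For death, SAP 10.4 plans Kaplan-Meier through day 365 with censoring at the last follow-up date. It then adds that "the frequency and percentage of deaths for any reason (all-cause mortality) will be presented with the two-sided 95% Wald confidence interval". SAP 10.2 also counts death in the morbidity and mortality composite, and it replaces a missing final mRS with the 7-day/discharge value.

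On missing data, SAP 12 says: "As sensitivity analyses, the primary effectiveness and primary safety endpoints will be recomputed using the ITT population after imputing missing data". On interim reporting, SAP 3 says: "However, interim analysis may be performed for the purpose of publication or regulatory submission of SURF results".

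Protocol 6.2 schedules one contact after the 7-day/discharge visit, at 1 year ± 90 days. SAP 2 states: "Approximately 800 patients will enroll in this post-market study, resulting in 720 patients who achieve final follow-up after 10% anticipated attrition".

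**The concern.** A missing occlusion grade shows up as missing. An SAE that nobody reported does not: the patient simply has no event form. The as-observed rule in SAP 12 therefore does not settle how a patient with no contact after discharge enters an event percentage. With ITT named as the population and no follow-up condition given, the natural programming choice is to divide by all enrolled patients and count the unobserved as non-events. That pushes the one-year rates downward.

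The plan would not reveal this for stroke or device-related SAE. The two primary safety endpoints are the only safety endpoints in the SAP 12 bounds. They close by the next calendar day or by discharge/day 7, before almost all the attrition. The censoring in SAP 10.4 applies to death alone. Time at risk also varies among completers, because the final visit may fall between day 275 (365 − 90) and day 455 (365 + 90).

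At stake is whether the reported one-year stroke and device-related SAE rates can be read as one-year risks. This matters most in an interim report, when many enrolled patients may not yet have reached one year.

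**Working it through.** **Inputs**
- Enrolment 800, with 720 reaching final follow-up (SAP 2).
- Attrition 10% (SAP 1).
- True one-year post-discharge risk *p*: the documents give no figure for stroke or for device-related SAE at one year, so 2% and 5% are assumptions.

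**1. The plan's own figures.** 800 × (1 − 0.10) = 720, as stated. The Wald interval for the primary device-related SAE endpoint also reproduces: 22/800 = 2.75%, with 1.96 × √(0.0275 × 0.9725/800) = 1.13 points, giving 1.62% to 3.88% against the stated 1.6% to 3.9%.

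**2. Crude ITT percentage under loss.** With 720 patients followed and 80 lost,

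crude rate = (720*p* + 80*q*)/800,

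where *q* is the part of a lost patient's risk captured before loss.

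- All loss at discharge and nothing captured: *q* = 0, so the crude rate is 0.90*p*.
- Loss uniform over the year with constant hazard: *q* = 1 − *p*/(−ln(1 − *p*)). For *p* = 5%, *q* = 1 − 0.05/0.05129 = 2.52%, and the crude rate is (36 + 2.02)/800 = 4.75%.

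| Assumed true risk | All loss at discharge | Uniform loss | Wald half-width, n = 800 |
|---|---|---|---|
| 2% | 1.8% | 1.9% | 0.97 points |
| 5% | 4.5% | 4.75% | 1.51 points |

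The relative understatement is therefore about 5% to 10% of the post-discharge part of the rate. Events before discharge are unaffected. A Kaplan-Meier or cumulative incidence estimate returns *p* if loss is unrelated to outcome.

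**3. Sensitivity to the attrition figure.** With all loss at discharge, *p* = 5% reads 0.80 × 5% = 4.0% at 20% attrition and 0.70 × 5% = 3.5% at 30%.

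**4. The bound that no planned output shows.** If the observed count were 40/800 = 5.0% (3.5% to 6.5%) and all 80 lost patients had events, the rate would be 120/800 = 15.0% (12.5% to 17.5%). This is an extreme bound, not an expectation.

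**The case against.** Much of the case on the other side is sound.

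- **The SAP never says that lost patients count as event-free.** SAP 8.1 and 8.2 use the same ITT phrase with evaluated-patient denominators, so the phrase alone does not fix the denominator at 800. This stands: the reading is an inference from the missing condition in SAP 10.2. If the sponsor intends something else, the denominator still has to be stated.
- **Events are reported as they occur.** Protocol 7.6.1 collects neurological SAEs after discharge and asks for device-related SAEs within 72 hours of site awareness. SAP 8.4 records additional follow-up visits and scans. This stands too, so multiplying the true rate by the fraction followed gives the largest understatement under non-informative loss, not the expected one. For the same reason, a reader should not infer that an interim report with half the patients followed would show half the true rate.
- **The endpoints are secondary and descriptive, and the final bias is small.** At an assumed 5% it is 0.25 to 0.5 points against a half-width of 1.5 points. Agreed.

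Three stronger readings are tempting but unsupported:

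- **That the missing-data analyses skip every endpoint exposed to attrition.** SAP 12 applies baseline, worst-case and best-case imputation to primary effectiveness at final follow-up. The gap concerns safety endpoints only.
- **That one-year mortality is mishandled.** SAP 10.4 already censors. Only the additional crude percentage and the death component of the composite share the problem.
- **That the predecessor registry measures the bias.** Protocol section 1 reports mortality of "0.4% (2/496) within 24 hours of intervention and 11.4% (21/185) after 24 hours". Setting 21/185 = 11.4% against 21/496 = 4.2% gives a ratio of 2.7, but 496 is the 24-hour mortality denominator, whereas the interim cohort was 500 subjects. One-year collection was still ongoing, and nothing shows 21/185 to be the true rate. That interim also used smaller denominators for later outcomes (185, 157, 140) and did not divide by all enrolled.

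**Conclusion.** The point holds for major ipsilateral stroke and for device-related SAE through the final visit. As written, these are crude ITT percentages with no follow-up condition, no censoring and no missing-data analysis, and stroke has no time window. At the planned 10% attrition, the post-discharge part is understated by about 5% relative under uniform loss and by at most 10% relative if all loss is at discharge with no events captured. An assumed true 5% would read 4.75% to 4.5%.

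These figures assume that loss is unrelated to outcome and that all 80 patients are lost rather than dead. The documents do not say whether the 10% includes deaths; if it does, the effect is smaller. Higher attrition, or loss related to outcome, could make it larger. So could an interim report made before most patients reach one year, but the documents give no interim timing or content from which to estimate by how much.

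This is a modest bias with an easy remedy, and it is worth correcting before database lock. It does not undermine the primary endpoints.

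**What to change.** In SAP 10.2:
- State the time window for major ipsilateral stroke.
- Estimate stroke and device-related SAE at day 365 by cumulative incidence, with death as a competing event and censoring at last follow-up, as SAP 10.4 already does for death.
- Show the crude count beside the number of patients followed to one year. Device-related SAEs after day 365 but by the final visit stay in that count.

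In SAP 10.4, make the Kaplan-Meier day-365 estimate the reported one-year mortality, with the crude percentage as a supplement.

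In SAP 3, require the same estimators in any interim report.

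Extending the SAP 12 best- and worst-case bounds to these endpoints is optional. For rare events the worst case is wide and says little beyond the number lost.

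The cost is SAP wording and slightly more analysis work, using event and last-follow-up dates the plan already relies on. No new data collection is needed. The stated one-year rates would become slightly less favourable.
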